9.1.7 Adverse Events

Potential adverse events are summarized in the Investigator's Brochure.

Study HuMax-Inflam-001: Safety in Participants with PPP

Within the dose range up to 8 mg/kg as a single-dose administration, the MTD of HuMaxInflam was not reached. Administration of HuMax-Inflam in a single dose of up to 8 mg/kg and up to 4 mg/kg in 4 weekly doses was safe and well tolerated by participants with PPP. Approximately 50% of reported AEs (45 of 85) were judged attributable to the study drug. The most frequent AEs were nausea, nasopharyngitis, and headache. There was no increase in the frequency of AEs with increasing dose. Administration of HuMax-Inflam did not lead to formation of antibodies against HuMax-Inflam.

Study CA027-001: Safety with BMS-986253 Monotherapy in Participants with Cancer

Multiple ascending doses of BMS-986253 were well tolerated across the dose range of 4 to 32 mg/kg Q2W in 15 adults with advanced tumors treated in Study CA027-001. AEs leading to discontinuation were reported in 3 (20.0%) participants, and all were considered not related to BMS-986253. AEs leading to discontinuation included Grade 3 increased blood alkaline phosphatase (ALP), Grade 2 increased blood creatinine, Grade 3 hypertension, Grade 3 fall, and Grade 3 back pain. There were no deaths due to AEs in this study. The MTD was not reached, and no DLTs were observed. There was 1 death due to disease progression within 48 days of the last dose of BMS-986253.

Five of the 15 participants were considered by the Investigator to have experienced AEs related to BMS-986253 monotherapy. All TRAEs were Grade 1 or Grade 2 in severity. The most common TRAEs were nausea (N = 2) and fatigue (N = 2). 1 patient treated at 16mg/kg with grade 1 “reduced white blood cells” related to study drug.

Study CA027-002: BMS-986253 plus Nivolumab in Advanced Cancers

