In the ongoing Study CA027-002 (data cut-off date of 16-Jan-2020), 92 participants have been treated with varying doses of BMS-986253 in combination with a flat dose of 480-mg nivolumab Q4W: 600 mg Q4W (N = 16), 1,200 mg Q4W (N = 15), 2,400 mg Q4W (N = 18), 1,200 mg Q2W (N = 12), and 2,400 mg Q2W (N = 31). Of these 92 participants, 9 received treatment as part of a safety lead-in: 5 received 2,400-mg BMS-986253 Q4W and 480-mg nivolumab Q4W, and 4 received 2,400-mg BMS-986253 Q2W and 480-mg nivolumab Q4W. All 9 participants dosed cleared a 28-day DLT period, with no DLTs observed. Overall, based on the available data as of 16-Jan-2020, no significant safety trends were identified.

Thirty of 92 (32.6%) participants experienced AEs related to the study drug combination. The most common TRAEs (N > 2) were Grade 1/2 fatigue (N = 9), Grade 1/2 nausea (N = 7), Grade 1 rash (N = 3), and Grade 1/2 decreased appetite (N = 3). Most TRAEs were Grade 1/2, and based on the available data, no dose-dependent TRAEs were identified. Of

note, 1 participant treated with Q2W BMS-986253 2,400mg experienced Grade 3 neutropenia on Cycle 2 Day 1; this participant was asymptomatic without evidence of infection, and the episode resolved without intervention in < 2 weeks. 2 patients experienced infusion reactions (1 patient grade 2 reaction and 1 patient with grade 4 infusion reaction).

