11.2.17 To characterize PK of BMS-986253

Will assess PK at screening, day 8, 15, 22, 29, and EOT by collection of serum at these time points when feasible. For patients ready for discharge prior to day 8, a serum sample should be collected, when feasible, prior to discharge.

Stopping Rules

The study may be discontinued by the data and safety monitoring committee (DSMC), the Food and Drug Administration (FDA), or other regulatory authorities. Any unforeseen deaths or serious adverse events may, after a discussion between the principal investigator, prompt an interruption to study accrual pending a full investigation into the circumstances surrounding the event.

Continuous Toxicity Monitoring

As this trial will be the first time an anti-IL-8 will be tested in patients with severe COVID-19, safety will be monitored on a continual basis. Sequential boundaries will be used to monitor dose-limiting toxicity rate.¹⁶ The accrual will be halted if excessive numbers of dose-limiting toxicities are seen, that is, if the number of dose-limiting toxicities is equal to or exceeds b_n out of n patients with full follow-up (see Table 3). This is a Pocock-type stopping boundary that yields the probability of crossing the boundary at most 0.05 when the rate of dose-limiting toxicity is equal to the acceptable rate of 30%. For the purposes of this stopping rule, dose-limiting toxicities will be defined as any treated related grade 3 or 4 toxicity.

Table 3. Toxicity Monitoring

Number of Patients, n	1	2	3	4	5	6-7	8-9	10-11	12-14	15-16	17-18	19-21	22-23	24-25	26-28	29-30	31-33	34-36	37-38
Boundary, b_n^*	-	-	-	4	5	6	7	8	9	10	11	12	13	14	15	16	17	18	19
Number of Patients, n	39-42-	44-	47-	50-	52-	55-	58-	60-	63-	66-	67-	71-	74-	77-	79-	82-	85-	98-	
	41	43	46	49	51	54	57	59	62	65	67	70	73	76	78	81	84	87	90
Boundary, b_n^*	20	21	22	23	24	25	26	27	28	29	30	31	32	33	34	35	36	37	38
Number of Patients, n	91-																		
	92																		
Boundary, b_n^*	39																		

*This boundary is equivalent to testing the null hypothesis, after each patient, that the event rate is equal to 30%, using a one-sided level 0.009 test.

For example, based on the boundaries above, if 12 out of the first 20 patients enrolled in the anti-IL-8 arm experience dose-limiting toxicities, the trial will be stopped for safety. In this case, the 95% exact confidence interval will be (0.36, 0.81), with the lower confidence limit exceeding the event rate (30%).

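### Table 3 accepts a 30% rate of related Grade 3-4 toxicity without explanation, well above the protocol's own safety figures, and two of its column headings are wrong

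*Combined protocol and SAP*

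**What the plan says.** Section 11, under Continuous Toxicity Monitoring, halts accrual "if the number of dose-limiting toxicities is equal to or exceeds b_n out of n patients with full follow-up". The events counted are defined thus: "dose-limiting toxicities will be defined as any treated related grade 3 or 4 toxicity". The boundary is Pocock-type, with a crossing probability of at most 0.05 "when the rate of dose-limiting toxicity is equal to the acceptable rate of 30" per cent. The footnote to Table 3 describes the same rule as testing, after each patient, "that the event rate is equal to 30%, using a one-sided level 0.009 test". No reason is given for 30%.

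The safety record is in section 9.1.7:

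- **CA027-001 (monotherapy, 15 patients).** Five had related events, and "All TRAEs were Grade 1 or Grade 2 in severity".
- **CA027-002 (with nivolumab, 92 patients).** "Thirty of 92 (32.6%) participants experienced AEs related to the study drug combination". Most were Grade 1 or 2. The text singles out one Grade 3 neutropenia, at 2,400 mg every 2 weeks, and two infusion reactions: "1 patient grade 2 reaction and 1 patient with grade 4 infusion reaction". It gives no total for Grade 3-4.

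In Table 3, the column with boundary 30 covers n = 66-67, the column with boundary 31 covers n = 67-70, and the column with boundary 38 is headed 98-90.

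**The concern.** The rate accepted for severe related toxicity (30%) is about the rate at which related toxicity of any grade, mostly mild, was seen: 5/15 = 33.3% and 30/92 = 32.6%. A boundary built on that null responds only when severe toxicity is well above 30%. The protocol introduces the rule because the drug class has not been tested in severe COVID-19, and Table 3 is its only numeric safety threshold. A reader who sees continuous monitoring may expect more sensitivity than the boundary has.

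Separately, a halting table should give one threshold for each n. At n = 67 this one gives two, and as printed no column covers n = 88, 89 or 90.

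**Working it through.** **Inputs.** From section 11: null rate 0.30, total crossing probability at most 0.05, per-look one-sided level 0.009, and the boundaries b_n of Table 3. From section 13.1: 92 patients in the anti-IL-8 arm. From section 9.1.7: 0/15, two named events in 92, and 31 patients in the 2,400 mg every-2-weeks group.

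**Method.** Let X_n be the number of patients with a dose-limiting toxicity among the first n. Start with P(X_0 = 0) = 1. For n = 1 to 92, update P(X_n = x) = (1 - p) P(X_(n-1) = x) + p P(X_(n-1) = x - 1). Add the probability at x >= b_n to the crossing total and remove it. The two doubtful headings are read as 68-70 and 88-90.

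**The plan's own figures.** At p = 0.30 the crossing probability is 0.0496, which agrees with the stated 0.05. The largest per-look tail is 0.0093 (n = 36), and a level of 0.0094 reproduces every entry, so 0.009 is a rounding. The exact interval for 12/20 is 0.361 to 0.809, as the protocol states. The arithmetic of the boundary is sound; the question is the null rate.

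**Crossing probability over 92 patients.**

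| True rate | P(cross) |
|---|---|
| 10% | 0.0001 |
| 20% | 0.0026 |
| 25% | 0.0106 |
| 30% | 0.0496 |
| 40% | 0.510 |
| 50% | 0.966 |

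At 40% the mean number treated over all trials is 67.78, counting trials that never stop as 92. Among trials that stop it is (67.78 - 0.4901 x 92) / 0.5099 = 22.69 / 0.5099 = 44.5. At a true 30%, 0.30 x 92 = 27.6 patients with such an event are expected if all 92 are treated. The observed proportion needed to halt is 12/20 = 60%, 22/46 = 48% or 39/92 = 42%.

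**Prior data, exact 95% intervals.**

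- 0/15: upper limit 1 - 0.025^(1/15) = 21.8%.
- 2/92 = 2.2%: 0.3% to 7.6%.
- 2/31 = 6.5%, if both named events fell in the 2,400 mg every-2-weeks group: 0.8% to 21.4%.

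On the named events, every upper limit is below 30%.

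**Table cells, binomial tails at 0.30.**

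- n = 67: P(X >= 30) = 0.0074, which meets the stated test; P(X >= 29) = 0.0145, which does not. The boundary at 67 is 30.
- n = 68: P(X >= 30) = 0.0096, which fails; P(X >= 31) = 0.0048, which passes. The 31 column starts at 68.
- Boundary 38 lies between 85-87 (boundary 37) and 91-92 (boundary 39), so its column can only be 88-90.
- Using 31 at n = 67 changes the crossing probability at 30% from 0.0496 to 0.0495.

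**The case against.** **The population differs.** The prior data come mainly from cancer patients. This trial admits ventilated and ICU patients with permissive laboratory limits, and section 3.1 puts mortality in severe disease at about 20-25%. A higher tolerated rate, to avoid false halts, can be a defensible risk-benefit judgement. That stands as a possible justification, but the protocol does not make the argument, and the rule counts only events judged related.

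**Other routes to a halt exist.** Under Stopping Rules, the DSMC or the FDA may discontinue the study, and deaths or serious events may interrupt accrual. The DSMC meets twice a month (section 12.3) and receives SAEs that are not unanticipated problems within 24 hours (section 8.4.3). This stands in full. A reader might infer from the table above that severe toxicity could not halt accrual. The documents do not support that: the probabilities describe the numeric boundary only.

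**The size of the mismatch is uncertain.** A reader might infer that a tenfold rise in severe toxicity would go unnoticed. Ten times 2/92 is 21.7%, where the boundary is crossed with probability 0.004. But 2/92 is only a floor, and it mixes dose groups. If the reference is 2/31, a tenfold rise is 65%, where a crossing is almost certain. No multiple is established.

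**A lower null is not a neutral remedy.** A boundary of the same type built on 20% would, by construction, be crossed only about 5% of the time at a true 20%. The data do not single out that figure or any other.

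**The cells may be extraction damage.** The sample-size headings of that block are split over two lines in the text available. Even so, 19 starts, 19 ends and 19 boundaries line up, and every other cell reproduces. The two headings should be checked against the source file.

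**Conclusion.** The point holds in a limited form. The boundary does what it claims at 30%, but 30% is unexplained and stands well above the severe-toxicity figures the protocol itself reports. The numeric rule is therefore close to inactive below 30% (at most about 1% at true rates up to 25%) and about even at 40%. The documents show a missing justification. They do not show that 30% is indefensible or that another rate is right.

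The probabilities assume independent patients with a common event rate, assessment after every patient with full follow-up, and 92 treated patients. The comparison with prior data rests on named events only.

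The cell errors hardly affect the overall crossing probability. They do leave contradictory or missing thresholds in a table that decides whether accrual halts.

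**What to change.** 1. Reconcile the 30% in section 11 with the figures in section 9.1.7. The sponsor and the DSMC should choose the acceptable rate and justify it, preferably with a full count of related Grade 3-4 events in CA027-002. If the rate changes, re-derive Table 3.
2. State the probability of crossing at several true rates, as tabulated above, and say that these apply to the numeric boundary alone.
3. Whatever rate is kept, correct the headings: boundary 30 for n = 66-67, boundary 31 for n = 68-70, boundary 38 for n = 88-90.

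The cost is a short justification, one small table and two corrected headings. If a lower rate is chosen, Table 3 must be recalculated, and accrual is more likely to be halted at intermediate toxicity rates. That trade-off belongs to the sponsor and the DSMC. No additional patients or data collection are needed.

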11.2 Secondary Endpoints

11.2.1 *Time to death*

The time to death will be defined as the time from onset from symptoms until death from any cause. Patients who are alive or lost to follow-up at the cut-off date will be censored from this analysis.

11.2.2 *Mortality at 1 month*

1-month mortality is defined as the percentage of patients who have died 1 month from the time of start of treatment.

11.2.3 *Time to intubation*

The time to intubation will be defined as the time from symptom onset until time of intubation. Any patients already intubated at enrollment will be censored from this analysis.

11.2.4 *Time to improvement in oxygenation*

The time to improvement in gas exchange will be defined as the time from time of start of treatment until a $\geq 30\%$ decrease in oxygen requirement compared to

baseline [or elimination of oxygen requirement] without a decrease in SpO2 sustained for at least 48hrs or until discharge.

11.2.4 *Proportion of patients requiring ICU admission at 1 month.*

The proportion of patients requiring ICU admission will be calculated as the number of patients requiring ICU admission over the course of their hospitalization over the number of evaluable patients.

11.2.5 *Safety and Toxicity*

All subjects receiving at least one dose of the study drug will be evaluated for safety by monitoring symptoms, physical examinations, and laboratory tests. Adverse events will be classified and graded according to the NCI Common Toxicity Criteria version 5.0 (see Appendix A). The absolute number and frequency of each adverse event will be reported, and subdivided according to toxicity grade. A description of adverse events by treatment arm will also be reported. A particular adverse event occurring more than once in the same subject will be counted only once and at its worse grade.

11.2.6 *Duration of Hospitalization*

Duration of hospital admission will be measured from the time of admission until the time of discharge.

11.2.7 *7-point Ordinal Scale Score*

The mean/medians of the 7-point ordinal raw scores at day 14 from the start of treatment will be computed and compared between the treatment and control groups.

Exploratory Endpoints.

11.2.8 *Change in inflammatory markers from baseline*

Changes in LDH, D-Dimer, CRP, ESR, NLR and absolute lymphocytes before and after treatment and over time will be measured every other day during hospitalization.

11.2.9 *Change in circulating sIL-6 levels from baseline*

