13 STATISTICAL CONSIDERATIONS

13.1 Study Design and Sample Size

This study is a single-center, randomized open-label phase 2 trial to evaluate the efficacy and safety of anti-IL-8 in hospitalized adults with severe or critical COVID-19. The primary endpoint is time to improvement in clinical status: the time (days) required from the start of treatment to the improvement of clinical status (2 points) assessment from baseline based on the 7-point ordinal scale. Patients for whom there was no event will be censored.

Patients will be randomized in a 2:1 allocation ratio to either anti-IL-8 or standard of care. Patients will be assessed daily while hospitalized. Discharged patients will be contacted by telephone on Day 29 and then monthly up to one-year to assess status. In addition to these specific assessment times, one interim analysis is planned at and the DSMC will actively monitor interim data to make recommendations about early signs of overwhelming efficacy and futility/study closure (see Section 13.4.)

With a sample size of 138 patients: N=92 patients randomized to the treatment arm and N=46 patients assigned to the standard of arm/control, the study will have 80% power to detect an increase in median time to improvement from 2 days (control) to 5 days (treatment arm) with one-sided alpha of 0.025. The sample size was estimated based on a hazard ratio (HR) of 0.40 assuming an exponential survival distribution with inflation to account for one interim look and 5% drop-out rate.

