18 ATTACHMENTS

APPENDIX A: COMMON TOXICITY CRITERIA, VERSION 5.0

Adverse events will be described and graded using the NCI Common Toxicity Criteria (Version 5.0). A copy of this document can be downloaded from the CTEP website (https://ctep.cancer.gov/protocolDevelopment/electronic_applications/ctc.htm). All treatment areas must have a copy of this document, or must be able to access a copy.

In general, the grading system can be summarized as follows:

Grade:	Severity:	Description:
Grade 1	Mild	Mild; asymptomatic or mild symptom; clinical or diagnostic observation only; intervention not indicated.
Grade 2	Moderate	Moderate; minimal, local or noninvasive intervention indicated; limiting age-appropriate instrumental ADL.
Grade 3	Severe	Severe or medically significant but not immediately life-threatening; hospitalization or prolongation of hospitalization indicated; disabling; limiting self-care ADL.
Grade 4	Life-threatening	Life-threatening consequences; urgent intervention indicated.
Grade 5	Death	Death related to an adverse event.

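### The numeric toxicity boundary (Table 3) counts only related grade 3 or 4 events, so a related death recorded as grade 5 does not move the trial toward it; deaths are left to a discretionary rule with no threshold.

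*Combined protocol and SAP*

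**What the plan says.** Section 11.2, under Continuous Toxicity Monitoring, gives a Pocock-type boundary in Table 3 for the anti-IL-8 arm. Accrual is halted when the number of dose-limiting toxicities reaches the tabulated value among patients with complete follow-up. The counted event is defined in one sentence: "dose-limiting toxicities will be defined as any treated related grade 3 or 4 toxicity".

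The rule is calibrated so that it "yields the probability of crossing the boundary at most 0.05" "when the rate of dose-limiting toxicity is equal to the acceptable rate of 30" per cent. The table footnote describes it as testing after each patient "using a one-sided level 0.009 test".

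Appendix A lists grade 5 separately from grades 3 and 4: "Death related to an adverse event". Sections 11.2.5 and 13.6 say that an adverse event recurring in the same subject "will be counted only once and at its worse grade".

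The Stopping Rules paragraph just above the boundary lets the DSMC, the FDA or other authorities discontinue the study, and adds: "Any unforeseen deaths or serious adverse events may, after a discussion between the principal investigator, prompt an interruption to study accrual". It gives no count or rate.

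**The concern.** The protocol justifies continuous monitoring by this being the first test of an anti-IL-8 in severe COVID-19. Table 3 is the only quantitative safety stopping rule; Table 4 in Section 13.4 monitors time to improvement. A numeric rule that counts severe and life-threatening related toxicity but omits fatal related toxicity has a gap at its most serious end.

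The wording looks like an oversight. Section 8.2 defines adverse events of special interest with an open upper end (grade 3 or greater), which takes in fatal events.

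The discretionary clause does not plainly fill the gap. It speaks of unforeseen deaths, and Section 3.1 cites a mortality of about 20 to 25% in severe disease, so it is not obvious which deaths qualify. It also names only one party to the discussion.

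**Working it through.** **Inputs.** Table 3 boundary; acceptable rate 30%, crossing probability at most 0.05 and nominal level 0.009 (Section 11.2); maximum of 92 monitored patients (Section 13.1: "N=92 patients randomized to the treatment arm"). Two ranges that are unclear in the table as read were taken as 68–70 (boundary 31) and 88–90 (boundary 38).

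**Method.** Let p be the probability that a patient counts as an event and b(n) the boundary at n patients. Let f(n,k) be the probability of k events at n patients without an earlier crossing. Then

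f(n,k) = f(n−1,k)·(1−p) + f(n−1,k−1)·p for k < b(n),

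and any mass at k ≥ b(n) is a stop at n. Summing the stops over n = 1 to 92 gives the stopping probability.

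**Step 1: reproduce the plan's figures.**
- At p = 0.30 the crossing probability is 0.0496, which agrees with at most 0.05.
- The largest nominal level on the boundary is 0.0093, at n = 36, which rounds to 0.009.
- The exact 95% interval for 12 of 20 is (0.361, 0.809), which agrees with the protocol's (0.36, 0.81).

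The boundary arithmetic is sound. The gap lies only in which events are counted.

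**Step 2: an example that needs no assumed rate.** For n = 19 to 21 the boundary is 12. Suppose that at n = 20 there are 11 patients with related grade 3 or 4 events and one whose only qualifying event is a related death, with no earlier crossing (for instance, the 11th event occurs at patient 19 and the death at patient 20).
- As written: 11 < 12, so accrual continues. If the patient who died is left out of n, then n = 19, the boundary is still 12, and accrual still continues.
- With grade 5 counted: 11 + 1 = 12, so accrual halts.

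**Step 3: effect on the stopping probability.** The documents give no rate of related deaths, so the rates here are assumptions. Take a 45% rate of related grade 3 to 5 toxicity with one fifth fatal: grade 5 is 0.45 × 1/5 = 9%, and grade 3 or 4 is 45% − 9% = 36%.

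| Handling of fatal cases | Stopping probability |
|---|---|
| Counted as events (p = 0.45) | 0.821 |
| As written, all enter n, none counted (p = 0.36) | 0.250 |
| As written, none enters n, none counted | 0.440 |
| As written, all enter n, half first counted at grade 3 or 4 (p = 0.36 + 0.045 = 0.405) | 0.545 |
| As written, all enter n, all first counted at grade 3 or 4 (p = 0.45) | 0.821 |

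Expected treated patients are 49 in the first row and 80 in the second.

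**Step 4: other assumed rates.** These take every fatal case to enter n and none to be counted at a lower grade.

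| Grade 3–4 | Grade 5 only | As written | Grade 5 counted |
|---|---|---|---|
| 30% | 5% | 0.050 | 0.199 |
| 30% | 10% | 0.050 | 0.510 |
| 30% | 20% | 0.050 | 0.966 |
| 20% | 20% | 0.003 | 0.510 |

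**The case against.** A reader might infer that a related death has no bearing on stopping, or that it always makes stopping less likely. The documents support neither.

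**Other routes exist.** The Stopping Rules paragraph lets a single death prompt an accrual pause and lets the DSMC or FDA close the study, whereas Table 3 cannot act before four events. Under Section 8.4, serious adverse events that are not unanticipated problems go to the DSMC within 24 hours, and unexpected fatal events go to the FDA within 7 days. Section 12.3 has the DSMC monitor every treated subject for toxicity and meet twice a month. This stands. It confines the point to the numeric boundary, but none of these routes supplies a threshold.

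**The direction of the effect depends on undefined terms.** Follow-up completeness is not defined for this rule, so a patient who dies may not enter n. Monitoring is continual and any related grade 3 or 4 toxicity counts, so a reaction that later proves fatal may already have been counted. The worst-grade convention governs adverse event summaries and is not expressly applied to Table 3. A patient with a separate related grade 3 or 4 event counts in any case. All of this stands and is why the result as written is a range.

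**The scenario is severe.** A 9% related death rate means about 0.09 × 92 = 8 drug-related deaths, and the comparison ignores any discretionary pause. Section 9.1.7 reports only grade 1 or 2 related events and no adverse-event deaths in CA027-001, and mostly grade 1 or 2 related events in CA027-002, though with one grade 4 infusion reaction. These were cancer patients, so the data are context only. The omission exists at any fatal share, but its size shrinks with that share.

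**Counting deaths adds limited protection.** At a total related grade 3 to 5 rate of 10% the crossing probability is 0.0001, and at 20% it is 0.003, even if every event were fatal. That is correct, and it is why the discretionary clause must remain.

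**Conclusion.** The point holds for the numeric boundary. Followed as written, Table 3 does not register a related toxicity recorded as grade 5, and deaths are left to discretionary action without a threshold.

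The 20-patient example shows the gap without any assumed rate; it requires only that the fatal event was not already counted at grade 3 or 4. In the assumed 45% scenario with one fifth fatal, counting deaths gives an 82% stopping probability, while the current text gives anything from 25% up toward 82%. The 25% figure is the extreme end: it needs a high fatal share, every fatal case entering n, and none first counted at a lower grade. It should not be quoted alone.

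**What to change.** In Section 11.2, define the event for Table 3 as any treatment-related toxicity of grade 3 or higher (grades 3 to 5). State that a patient with a fatal related event enters both n and the count, which also settles how completeness of follow-up applies to patients who die. Keep the discretionary death clause alongside the boundary.

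The cost is a change of one phrase and one added sentence. Table 3 depends only on the 30% reference rate and the nominal level, so it needs no recalculation provided the sponsor confirms that 30% is the acceptable rate for grades 3 to 5 together. If 30% was meant for grades 3 and 4 alone, the sponsor must state the rate intended for the wider definition and regenerate the table from it. Sample size and the efficacy analysis are unaffected.

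### Table 3 prints two toxicity boundaries at n = 67 and an impossible range for n = 88–90; a minor correction to a safety decision table, largely resolvable from its own footnote

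*Combined protocol and SAP*

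**What the plan says.** Section 11 (Continuous Toxicity Monitoring) halts accrual "if the number of dose-limiting toxicities is equal to or exceeds b_n out of n patients with full follow-up", with b_n read from Table 3. The boundary is described as Pocock-type, with "probability of crossing the boundary at most 0.05 when the rate of dose-limiting toxicity is equal to the acceptable rate of 30" per cent. The footnote gives the generating rule: "This boundary is equivalent to testing the null hypothesis, after each patient, that the event rate is equal to 30" per cent, "using a one-sided level 0.009 test". The table runs to n = 92, which matches Section 13.1: "N=92 patients randomized to the treatment arm". The worked example is that "if 12 out of the first 20 patients enrolled in the anti-IL-8 arm experience dose-limiting toxicities, the trial will be stopped for safety", with an exact 95% interval of (0.36, 0.81).

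The second block of Table 3 lists 19 range starts, 19 range ends and 19 boundaries (20 to 38). Paired in order, the cells that matter are:

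| Range as printed | Boundary |
|---|---|
| 66–67 | 30 |
| 67–70 | 31 |
| 71–73 | 32 |
| 85–87 | 37 |
| 98–90 | 38 |
| 91–92 (third block) | 39 |

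**The concern.** A rule applied after every patient needs exactly one boundary at each n. The printed table gives two at n = 67. The range 98–90 is empty, so n = 88 and 89 are in no column, and n = 90 appears only as the end of a range that cannot exist. All these counts lie within the planned 92-patient arm.

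Table 3 is the only numeric toxicity stopping rule in the documents, and its output is a decision to halt or continue accrual. With 30 dose-limiting toxicities among 67 evaluable patients, the 66–67 column halts and the 67–70 column continues.

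**Working it through.** **Inputs**, all from Section 11 unless stated: acceptable rate 0.30; one-sided per-look level printed as 0.009; a look after each patient; halt when the count is at least b_n; overall crossing probability at most 0.05; maximum n = 92 (Section 13.1).

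**Formulas.** The boundary b_n is the smallest r with P(X ≥ r) ≤ level, where X ~ Binomial(n, 0.30). For the overall crossing probability, let f_n(k) be the probability of having k toxicities after n patients without having crossed. Then f_n(k) = 0.7·f_{n−1}(k) + 0.3·f_{n−1}(k−1) for k < b_n. Any mass that reaches k ≥ b_n is added to the crossing total, summed over n = 1 to 92.

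**Step 1: the plan's own figures.** At n = 20, P(X ≥ 12) = 0.0051, and the rule gives b_20 = 12. The exact 95% interval for 12/20 is (0.361, 0.809). Both agree with the worked example. With 30 at n = 67 and 38 at n = 88–90, the overall crossing probability at 30% is 0.0496, within the stated 0.05.

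**Step 2: coverage.** Expanding every printed range from n = 4 to n = 92 gives exactly one boundary at each n except n = 67 (30 and 31) and n = 88, 89 and 90 (none). The dashes at n = 1–3 are deliberate: three toxicities in three patients has probability 0.3³ = 0.027, above the level.

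**Step 3: what the rule gives at the faulty cells.**

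| n | Tail one below | Tail at boundary | Boundary |
|---|---|---|---|
| 67 | P(X ≥ 29) = 0.0145 | P(X ≥ 30) = 0.0074 | 30 |
| 68 | P(X ≥ 30) = 0.0096 | P(X ≥ 31) = 0.0048 | 31 |
| 88 | P(X ≥ 37) = 0.0109 | P(X ≥ 38) = 0.0060 | 38 |
| 89 | P(X ≥ 37) = 0.0133 | P(X ≥ 38) = 0.0074 | 38 |
| 90 | P(X ≥ 37) = 0.0162 | P(X ≥ 38) = 0.0092 | 38 if the level is at least 0.0092; 39 at a literal 0.009 |

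**Step 4: which level the table uses.** Each clear entry needs P(X ≥ b_n) ≤ level < P(X ≥ b_n − 1). The tightest lower limit is at n = 36, where P(X ≥ 18) = 0.00928. The tightest upper limit is at n = 26, where P(X ≥ 14) = 0.00944. Any level from 0.00928 up to just below 0.00944 reproduces every clear entry, and gives 30 at n = 67 and 38 at n = 88–90. A literal 0.0090 gives a boundary one higher than printed at n = 36, 49, 57 and 76. A level of 0.0095 fails the other way, at n = 12 and n = 26.

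**Step 5: size of the effect.** Overall crossing probability at a 30% rate:

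| At n = 67 | 38 at n = 88–90 | No look at n = 88–90 |
|---|---|---|
| 30 | 0.0496 | 0.0493 |
| 31 | 0.0495 | 0.0492 |

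With 38 at n = 88–90, using 30 rather than 31 at n = 67 moves the crossing probability from 0.5095 to 0.5099 at a 40% rate, and from 0.8211 to 0.8213 at 45%. The chance of arriving uncrossed at exactly 30 of 67 is about 0.03% at a 30% rate, 0.7% at 40% and 0.9% at 45%. Dropping the looks at 88 and 89 but keeping 38 at n = 90 changes the overall probability by zero, because a count that has reached 38 is still at least 38 at n = 90.

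**The case against.** Four points can be made against this.

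- **It may be a reading error.** The second block was extracted from PDF with visible damage (two starts, 39 and 42, run together), and both suspect values differ from the expected ones by a single digit involving an 8. The matching 19/19/19 counts, with every other pair contiguous and in line with the binomial rule, rule out a column shift. They do not rule out a misread digit, so this part stands and the source page must be checked.
- **The document resolves the gap itself.** A reader might infer that the rule cannot be applied at these counts, or that no threshold exists at n = 88 and 89. The documents do not support that. The footnote's test gives 30, 38 and 38 at n = 67, 88 and 89 even at a literal 0.009, and the neighbouring cells (37 through n = 87, 39 from n = 91) leave only 38 between them. What remains is n = 90, where the rounded level and the table's implied level disagree.
- **The effect is negligible.** This stands in full for operating characteristics. It does not remove the conflict at 30 of 67.
- **Accrual may be over by then.** The rule counts patients with full follow-up, and the toxicity window is not defined. If it is the 100-day period of Section 8.2, Table 4's expectation of N = 138 at month 2.6 (about 79 days, at 30.4 days a month) would put the end of accrual before these counts are reached. That depends on an assumed window. Even with a short window, at n = 88 no more than four patients (92 − 88) remain to be enrolled. This limits the consequence but does not make the table correct.

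**Conclusion.** The defect holds as a minor one. Table 3 as printed is double-valued at n = 67 and has an impossible range where n = 88–90 should be. The practical conflict is confined to 30 toxicities in 67 patients. At n = 88–89 the worst case is a short delay to n = 90, provided that 38 is applied there.

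A reader might go further and infer that the safety rule loses its error control. It does not: the overall crossing probability at a 30% rate is 0.049–0.050 under any reading of the faulty cells, inside the stated 0.05.

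The footnote does not fully replace the table, because a literal 0.009 gives 39 at n = 90 and disagrees with the printed boundaries at n = 36, 49, 57 and 76.

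The conclusion rests on the two digits (67 and 98) being on the original page, and on the exact binomial test described in the footnote.

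**What to change.** Confirm the two digits on the source page. If they stand, change the two range starts so that the columns read 68–70 (31) and 88–90 (38), leaving 66–67 (30) as it is. In the footnote, state the per-look level to more decimals (about 0.0093–0.0094), so that the rule reproduces the whole table, including n = 36, 49, 57, 76 and 90. If the digits prove to be a reading error, only the footnote change remains.

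The cost is two table cells and one footnote figure. Design, sample size and analysis are unaffected, and the overall crossing probability of the corrected table is 0.0496.
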